### **7.4. Statistical Plan**

This is a pilot study looking at using DBS in 10 Tourette Syndrome patients.

### **7.5. Early Stopping Rules**

Date: 2/24/2021

Principal Investigator: [name], PhD

Application Number: NA\_00073086

DBS will be discontinued if the subject experiences a worsening of his tic or other Tourette symptoms (or OCD, ADHD, depression, or anxiety symptoms) without returning to baseline (prior to DBS implantation) within 4 weeks from the worsening of the symptoms. DBS will be discontinued if subjects experience suicidal ideation or mania that does not improve with turning off the stimulator. DBS will also be discontinued if neurologic symptoms including muscle contractions, flashing lights, electric jolting sensations, increase in dyskinesias will not improve with stimulator setting change and they are severe enough to interfere with patient daily functioning. Finally DBS will be discontinued if subjects are unable to tolerate the stimulator for any reason not foreseen by the investigator and that clearly interferes with subject's functioning.

Subjects will also be removed from the study for any significant adverse events that jeopardize patient safety. This includes any events related to the surgical procedure or subsequent DBS stimulation therapy. The entire study of 10 subjects will be stopped should the number of subjects meeting the above **Early Stopping Rules** reaches 3 at any point in the study. If this occurs before the full subject recruitment goal has been met, no further subjects will be recruited.

## 7.6. Data Sharing

De-identified information regarding the implanted subjects will be shared with the TAA International DBS Database (IRB#201600091) at the University of Florida Center for Movement Disorders & Neurorestoration in Gainesville, FL. Elements to be transferred, where available, include:

Year of birth;

Gender;

Ethnicity;

Age at onset;

Age at diagnosis;

Age at surgery;

Pre-operative psychiatric comorbidities;

Pre-operative medications;

Pre-operative outcome measures/severity ratings [depending on what you use, be specific here];

Surgical target & hardware implanted;

Post-operative lead location measurements;

Post-operative programming parameters;

Post-operative outcome measures/severity ratings [again, specific];

Information regarding Adverse Events (start date, end date, relevant medications and diagnostic findings, narrative summaries, etc.)

The information is being gathered in order to permit broader analysis of the trends and outcomes in DBS surgery for TS than is possible at any one institution. Collaborators to the project are registered with the UF Identity Management system and given secure 'Gatorlink' credentials which can be used to access the database for entry and review of data. The de-identified data, in an organized spreadsheet, may also be sent to the study team at the University of Florida for entry into the database.

## 8. Risks

### 8.1. Medical risks

Date: 2/24/2021

Principal Investigator: [name], PhD

Application Number: NA\_00073086

The medical risks of this study are the same as for other types of DBS surgery: bleeding, stroke, paralysis, infection, and death. The risks of anesthesia include heart attack, arrhythmia or allergic reaction. The risks associated with the System are failure of therapy, neurologic symptoms including muscle contractions, electric jolting sensations, speech alterations, and altered ability to think or remember. Most of these can be reversed by adjusting the stimulator. To be included in this protocol patients/their parents must sign a Hospital consent form listing these risks. Additionally this form will state that the FDA has not approved this indication for the use of the System, which is itself FDA approved. There may be side effects and discomforts that are not yet known.

## 8.2. Adverse events associated with DBS

There is a small but serious risk of intracranial hemorrhage with implantation of the lead, which is substantially lower than the risk associated with ablative procedures such as pallidotomy (39). A review of the literature estimated that rates of symptomatic and asymptomatic intracranial hemorrhage in DBS of the STN are ~ 2% and 1.2%, respectively (40) and infection occurs in ~ 2% of cases. The mortality rate for the procedure is below 1% and is mostly due to intracranial hemorrhage. One large multicenter report of 1,183 patients who received DBS reported a 30-day postoperative mortality rate of 0.4% (41). Other reported complications included hardware problems such as generator failure or lead breakage (6%—9/149), stimulation-induced side effects (3%—4/149), and behavioral changes (1%—2/149) (42). The infection rate is no higher than for other surgical procedures, but if it does occur, it can necessitate the explantation of the device or generator (43).

Deep brain stimulation can cause brain tissue damage if the stimulation charge density exceeds 30  $\mu\text{C}/\text{cm}^2/\text{phase}$ . The stimulation settings used in this study (similar to the current FDA approved DBS indications) will not exceed this limit.

The accuracy of electrode placement in DBS implantation surgery is optimized by using a series of overlapping and independent targeting methods. First, the patients wear a rigid stereotactic head frame (Leksell Frame, Elekta AB, Stockholm) which defines a Cartesian stereotactic space within the fiducial volume of the frame. Patients undergo MRI head imaging (or CT imaging if there are MRI contraindications) immediately after frame placement. It is also possible to use post-frame placement CT images fused to a previously obtained MRI head series for targeting minimizing the time spent wearing the stereotactic frame during the imaging process. Stereotactic frames are fitted with fiducial markers which appear bright in standard MRI T1- or T2-weighted images, or radiopaque markers for CT scans. There are several commercially available software packages which then convert screen pixel location defined by a cursor to the Cartesian space defined by the frame (Leksell SurgiPlan, Elekta AB, Stockholm; FrameLink, Medtronic, Minneapolis). Either direct targeting of the target structure can be performed by placing the cursor over the targeted structure, or the target structure can be inferred by the relatively fixed positions of atlas-based brain landmarks such as the well-known anterior commissure – posterior commissure system. The final coordinates for the target are then set on the appropriate x, y, and z graduated markings built into the frame system.

As a check on the imaging derived target location, microelectrode recording will be performed, as in the treatment of movement disorders where the targets include the subthalamic nucleus, the globus pallidus interna, and subnuclei of the thalamus. These structures have well-known and well-defined extracellular electrophysiologic firing patterns. The surgeon will use these firing patterns to help in verifying the electrode tip location, and to help in deciding where the tip should be moved if the firing patterns are consistently different from the known target firing patterns. Additionally, stimulation currents are used

Date: 2/24/2021

Principal Investigator: [name], PhD

Application Number: NA\_00073086

(passing through the microelectrode guide tube) and can aid in defining possible side effects due to the stimulation currents from the final implanted electrode and can guide the movement of the electrode on subsequent passes to optimize placement in the thalamus while minimizing sensory or motor side effects due to the applied stimulation.

Standard risk reduction efforts in the operating room will be implemented as in other surgical procedures. The federally mandated Safety Pause will be performed before skin incision, which includes patient verification, surgical site verification, and a team discussion of unusual case aspects. The equipment packs will be opened on the sterile field before skin incision to check for any sterility or operational issues. Intravenous antibiotics will be administered to the patient within 30 minutes of skin incision, followed by two postoperative doses for the stage of the procedure involving intracranial electrode placement. A single preoperative dose of antibiotics will be given within 30 minutes of skin incision for the implantation of the implantable pulse generator. Electrode placement will additionally be checked in the operating room using a fluoroscopic unit which has been draped into the field. A lateral fluoroscopic image will include the electrode tips and their location with respect to the frame fiducials showing the center of the frame coordinate system. Postoperative imaging will include an immediate head CT examination as the patient leaves the operating room, and a delayed MRI of the brain. Both scans are to verify final electrode location and to look for any perioperative complications (i.e. hemorrhage, lead migration / breakage).

### **8.3. Plans for reporting unanticipated problems or study deviations**

The PI of the study will be responsible for reporting all adverse events to the IRB. Serious adverse events deemed to be associated with the study device (adverse device effect) will be reported to the IRB within 7 days. Any deaths will be reported within 24 hours.

Adverse device effects (ADEs) in this study are identified and categorized in a way patterned after the Code of Federal Regulations (21 CFR 812.3):

a. An adverse device effect (ADE) is any serious adverse effect on the health and/or safety or any life threatening problem or death caused by, or associated with the device and/or stimulation therapy if that effect, problem or death was not previously identified in nature, severity, or degree of incidence in the application; or any other unanticipated serious problem associated with a device that relates to the rights, safety, or welfare of subjects (21 CFR 812.3):

- i. The implanted components (lead, extension, neurostimulator)
- ii. The lead/extension tract or neurostimulator pocket
- iii. The burr hole site

b. An event will not be considered related to the device when it is the result of:

- i. A preexisting medical condition
- ii. A medication

Furthermore, AEs will be further categorized and identified as Surgical/Procedure Related, Device Related, Therapy Related, Disorder Related, or Other/Procedure Related. Examples of each of these categories may include (but are not limited to):

Surgical/Procedure Related – surgical site infection, perioperative mental status changes, perioperative confusional state or delirium, perioperative syncope, perioperative adverse drug reactions, cerebral hemorrhage, perioperative stroke, perioperative pulmonary embolism, etc.

Date: 2/24/2021  
Principal Investigator: [name], PhD  
Application Number: NA\_00073086

Device Related – Lead fracture, lead migration, implantable pulse generator failure or abnormal function, skin erosion or delayed infection, etc.

Therapy Related – gait disturbance or balance disorder, confusional state or delirium not attributable to medication or other health problem, mental status changes not attributable to medication or other health problem, problems with speech, depression and suicidal ideation, induced dyskinesias, etc.

Other/Procedure Related – Falls or balance disorder, pneumonia, syncope, confusional state or delirium, mental status changes, depression and suicidal ideation, adverse drug reactions, etc.

Disorder Related – falls or balance disorder, gait disturbance, depression and suicidal ideation, etc.

The severity of AEs will be classified after the scheme of Follett et al. (44) – as serious adverse events (an event that poses substantial risk to the patient's health and is likely to require medical intervention or close follow-up), and moderate or severe adverse events (an event that may interfere with normal activity and lead to the consideration of medical intervention or close follow-up).

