### **7.3. Safety Analysis**

Safety will be assessed by recording the frequency and severity of adverse events, defined as any new symptom or worsening of a pre-existing symptom. Adverse events reported on case report forms will be mapped to preferred terms and body systems using the Medical Dictionary for Regulatory Activities (MedDRA) coding dictionary. The number and percent of subjects reporting each event will be summarized during the study period. Incidence of adverse events by maximum reported severity will also be tabulated. Serious adverse events and adverse events leading to discontinuation will be displayed.

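### Section 8.3 grades adverse events only as serious or as a merged moderate-or-severe class, which does not fit the maximum-severity table planned in Section 7.3

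*Combined protocol and SAP*

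**What the plan says.** Section 2.1 makes safety one of the two primary objectives. Section 7.3 says how it is read out: "Safety will be assessed by recording the frequency and severity of adverse events". Its definition of an adverse event is wide, "defined as any new symptom or worsening of a pre-existing symptom", and carries no severity threshold. Three kinds of summary are planned there:

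- the number and percentage of subjects with each event;
- a severity table: "Incidence of adverse events by maximum reported severity will also be tabulated";
- a separate display: "Serious adverse events and adverse events leading to discontinuation will be displayed".

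The severity scheme itself stands at the end of Section 8.3, after the causal categories. It follows a cited trial of stimulation in Parkinson's disease and has two classes. The upper one takes events "as serious adverse events (an event that poses substantial risk to the patient's health and is likely to require medical intervention or close follow-up". The other is "moderate or severe adverse events (an event that may interfere with normal activity and lead to the consideration of medical intervention or close follow-up".

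Earlier in Section 8.3 the word serious also sets a reporting clock: "Serious adverse events deemed to be associated with the study device (adverse device effect) will be reported to the IRB within 7 days". No other severity scale for adverse events appears in the document. The word mild is used only for deficits in decision-making capacity (Section 4.2), and milder only for forms of the disease (Section 1).

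**The concern.** A table by maximum severity needs an ordered scale on which every adverse event has a place. Section 7.3 collects events without a lower limit, but the Section 8.3 scale starts at moderate. It gives moderate and severe one shared definition, and its top level is a different attribute: seriousness is about risk to health and the need for intervention, while severity is about intensity.

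The stake is the readability of one part of the safety report. Section 7.4 is a single sentence, so the summaries in Section 7.3 are the whole safety analysis. Low-grade events are to be expected. Adverse events are checked at every visit from 4 to 13 (Section 4.12), programming is adjusted over the same period, and Section 8.1 says that most effects of the system can be reversed by adjustment. Someone reading the table would want to tell a brief, tolerable stimulation effect from one that limits activity.

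**Working it through.** The plan gives no figure to reproduce. The check is to take each kind of event that Section 7.3 admits and look for its class in Section 8.3.

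| Event | Adverse event under 7.3? | Class under 8.3 | Effect on the severity table |
|---|---|---|---|
| Does not interfere with activity, no substantial risk | Yes | None | Left out, or graded up to moderate or severe |
| Moderate, not serious | Yes | Moderate or severe | Cannot be told from the next row |
| Severe, not serious | Yes | Moderate or severe | Cannot be told from the row above |
| Serious, of any intensity | Yes | Serious | Intensity not captured |

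Three things follow.

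1. The first kind of event meets the definition of an adverse event but neither class definition.
2. The table can have at most two rows under the stated scheme. Even if a form used moderate and severe as separate labels, Section 8.3 gives no criterion for choosing between them.
3. The upper row is the set of serious events, which Section 7.3 already displays separately. That row therefore adds little, and the intensity of those events appears nowhere.

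Size for a by-subject table:

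- N = 10 subjects (Section 7.4).
- k = number of subjects whose events are all mild. The documents give no figure, so k is an assumption.
- If those subjects are graded up, the moderate-or-severe row is too high by 100 × k / N = 100 × k / 10 = 10k percentage points. If they are left out, the same share of subjects is missing from the table.
- k = 0 gives 0 points, k = 1 gives 10, k = 2 gives 20, and so on by 10 for each further subject.

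A subject with a mild event and also a worse one does not move this row, because the worse event sets the maximum. Section 7.3 does not say whether the table is by subject overall or by event term. If it is by term, the same 10 points apply to each term that a subject had only in mild form.

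**The case against.** There is a fair case that this matters little.

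- **The case report form may hold a fuller scale.** Section 7.3 refers to reported severity, and the form is not part of the document. The scheme is also said to follow a cited trial, so the two definitions may be a summary. This stands as a limit: one cannot say that events will be misgraded, only that the written rule leads there. If the form does have a mild grade, Section 8.3 disagrees with it and still needs correcting.
- **The lower class is defined by what may interfere with activity.** That is a low threshold and could take in many slight symptoms. The group without a class may be small, but it is not empty.
- **The rest of Section 7.3 limits the harm.** The count of subjects with each event has no severity filter. A reader might infer that mild events would disappear from the safety record. They would not; they could be missing only from the severity table.
- **Every serious or activity-limiting event has a class.** A reader might infer that a serious event of moderate intensity and a severe non-serious event cannot both be placed. They can: the first is serious and the second is moderate or severe. What is lost is detail on intensity.
- **No decision hangs on the split.** A reader might infer that stopping or reporting is compromised. The stopping rules in Section 7.5 use their own clinical criteria. In Section 8.3 all adverse events go to the IRB, and the faster timelines depend on device-associated seriousness or on death.

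These points narrow the consequence. They do not remove the mismatch between the two sections.

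**Conclusion.** The point holds in a limited form. The severity rule in Section 8.3 is defective as stated: it has no mild class, does not separate moderate from severe, and treats seriousness as a level of severity. It cannot produce a sound version of the table that Section 7.3 promises.

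The effect is confined to that descriptive table; no hypothesis test or sample size is involved. Its size is 10 percentage points for each subject whose only events are mild, if the table is by subject. The documents do not support any particular total, because they do not indicate how many such subjects to expect. The conclusion assumes that the two classes in Section 8.3 are the scheme actually used to grade events. It is worth correcting because safety is a primary objective and the correction is cheap.

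**What to change.** In Section 8.3, and on the case report form if it does not already do so, record two separate items for every adverse event:

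- severity, as mild, moderate or severe, each defined by the degree of interference with normal activity;
- seriousness, as yes or no.

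In Section 7.3, state that the maximum-severity table is built from the first item and the serious-event display from the second, and say whether the severity table is by subject overall or by event term.

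The cost is a change of wording and possibly one field on the form. Events already recorded would have to be regraded from their narratives where these are available; Section 7.6 lists narrative summaries among the adverse-event data to be shared. Events whose narrative does not allow a grade should be shown as ungraded, so that the table still accounts for all of them.

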#### **8.4. Disclosing reportable findings and parental notification**

The following set of ground rules to use in terms of informing parents of the 15-17 year age range study subjects about concerning results from the psychiatric assessments, or revelations of high risk behaviors will be implemented in this study:

We assess for suicidal thoughts at multiple visits in the protocol (using the CSSS), if we are concerned about the child based on the answers to this assessment, the parents will be informed and a discussion will be had with the parents and the child to gain more information. Additional treatment providers will be contacted (child psychiatry) if the child does appear to be at risk of hurting himself/herself.

Assessments during the study visits also include questions concerning drug and alcohol use. This information will be kept private and not disclosed to the parent or authorities unless there are serious concerns about the child's safety or the safety of others. If the child provides study staff with information indicating that imminent harm to self and/or others is possible as a result of drug and alcohol use (for example, substance use while driving, binge behaviors, risky and unprotected sexual contact under the influence, etc.), then the parents will be informed.

Any information regarding child abuse, reportable communicable diseases, and any possible threats of harm to the subject or others (for example suicide and homicide) will be disclosed to the parent(s) or the appropriate authorities depending on the circumstance.

#### **8.5. Legal risks (e.g. associated with breach of confidentiality)**

N/A

#### **8.6. Financial risks to the participants**

There are no financial risks to the study's participants

### **9. Benefits**

JHMIRB eFormA 01  
Version 3 Dated: 06/2007

Date: 2/24/2021  
Principal Investigator: [name], PhD  
Application Number: NA\_00073086

As this is a pilot study, the probable benefits for the participant and for society are unknown. However, if DBS of the thalamic Ce-Spv-Voi complex results in improvement in tic frequency or severity, this could result in an improvement in the quality of life of patients with treatment-refractory Tourette Syndrome. These patients face long term social stigma and difficulties with education and job attainment. A new therapeutic treatment option could result in improvements in social integration. Additionally, information about stimulation of the brain in patients with TS along with microelectrode recordings obtained during the surgical placement procedure may improve treatment for future patients.

## **10. Payment and Remuneration**

No payment is scheduled for the patient's participation in this study.

## **11. Costs**

Portions of this research study are supplied free of charge to the patient. These include the baseline physical examination, the baseline EKG, the baseline clinical laboratory tests, the urine toxicology screen, and the urine pregnancy test if needed. The subject and/or their health insurer is responsible for all other parts of the study as identified in the Johns Hopkins Prospective Reimbursement Analysis as performed by the Clinical Research Support Services Office. The Centers for Medicare and Medicaid Services has given us permission to bill Medicare Part A and Part B for these portions of the study.

